7 STATISTICAL ANALYSES

7.1 General Methods

Unless otherwise noted, discrete variables will be tabulated by the frequency and proportion of subjects falling into each category, grouped by treatment. Percentages given in these tables will be rounded to the first decimal and, therefore, may not always sum to 100%. Percentages less than 0.1 will be indicated as '< 0.1'. Continuous variables will be summarized by treatment group using the mean, standard deviation, median, minimum, and maximum values.

Time-to-event variables (e.g. time-to resolution) will be analyzed using the Kaplan-Meier technique. When specified, the median will be reported along with 95% CI using Brookmeyer and Crowley method⁵ (using log-log transformation for constructing the confidence intervals⁶).

Unless otherwise specified, the stratified log-rank test will be performed to test the comparison between time to event distributions. Unless otherwise specified, the stratified hazard ratio between 2 groups along with CI will be obtained by fitting a stratified Cox model with the group variable as a unique covariate.

Confidence intervals for binomial proportions will be derived using the Clopper-Pearson method.⁷ The unweighted difference in ORRs between the two treatment arms and corresponding asymptotic 95% CI will be estimated using a Newcombe method.⁸

P-values from sensitivity analyses for efficacy endpoints are for descriptive purpose only and there will be no multiplicity adjustment for these analyses.

The conventions to be used for imputing missing and partial dates for analyses requiring dates are described in [Section 8](#).

Note that, the outputs will present Arm A, Arm B, and Arm C in the following way:

- All analysis specified in [Section 7.3](#) and [7.4](#) will present A, B, and C together.
- For purposes of efficacy analyses, all randomized subjects in Arm A and Arm C will be tabulated and presented in the same table. A few separate efficacy summary tables will be generated for those subjects randomized to Arm B, which will be specified in the corresponding sections.
- For purposes of safety analyses, all treated subjects in Arm A and Arm C will be tabulated and presented in the same table. A few separate safety summary tables will be generated for those subjects treated in Arm B, which will be specified in the corresponding sections.
- Summaries of outcome research and biomarker data will be tabulated on the Arm A and C subjects only.

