7.6.6.3 Time-to Resolution of Select AE

Time-to resolution of the following specific events will be summarized separately for each category/subcategory.

- Time-to resolution of drug-related select AE (any grade, grade 3-5) by treatment group
- Time-to resolution of drug-related select AE (any grade, grade 3-5) where immune modulating medication was initiated, by treatment group

Time-to resolution analyses are restricted to treated subjects who experienced the specific events. Time-to resolution where immune modulating medication was initiated analyses are restricted to treated subjects who experienced the specific events and who received immune modulating medication during the longest select AE.

The analyses will be conducted using the 30-day safety window.

The following summary statistics will be reported: percentage of subjects with resolution of the longest select AE, median time-to resolution along with 95% CI (derived from Kaplan-Meier estimation) and ranges.

See time-to resolution definition subsection of [APPENDIX 1](#) for additional details.

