7.6.7 Immune-Mediated Adverse Events (US Submission)

IMAEs will be summarized by treatment group for each immune-mediated category / PT using the 100-day safety window:

- Overall summary of non-endocrine IMAEs by worst CTC grade (any grade, grade 3-4, grade 5) where immune modulating medication was initiated presented by Category / PT.
- Overall summary of endocrine IMAEs by worst CTC grade (any grade, grade 3-4, grade 5) presented by Category / PT.
- Overall summary of non-endocrine IMAEs leading to discontinuation by worst CTC grade (any grade, grade 3-4, grade 5) where immune modulating medication was initiated presented by Category / PT.
- Overall summary of endocrine IMAEs leading to discontinuation by worst CTC grade (any grade, grade 3-4, grade 5) presented by Category / PT.
- Overall summary of non-endocrine IMAEs leading to dose delay or reduction by worst CTC grade (any grade, grade 3-4, grade 5) where immune modulating medication was initiated presented by Category / PT
- Overall summary of endocrine IMAEs leading to dose delay or reduction by worst CTC grade (any grade, grade 3-4, grade 5) presented by Category / PT.
- Summaries of time-to onset and time-to resolution of non-endocrine IMAEs where immune modulating medication was initiated presented by Category.
- Summaries of time-to onset and time-to resolution of endocrine IMAEs presented by Category.

A by-subject listing of IMAEs will be provided. By-subject listings of time-to resolution for longest IMAEs cluster (any grade and grade 3-5 in separate summaries) will also be provided. For new studies which collect investigator assessment of potential IMAE data, a by-subject listing of AEs considered as immune-mediated events per investigator but not qualified for IMAEs definition will also be provided.

In addition, for all nivolumab treated subjects who experienced at least one IMAE, the following data presentation will be provided:

- Summary of subjects who were re-challenged with nivolumab by IMAE category, with extended follow-up
- Summary of subjects who were re-challenged with nivolumab or ipilimumab by IMAE category, with extended follow-up

For these, re-challenge is considered to have occurred when last nivolumab and/or ipilimumab infusion was administered after the onset of an IMAE.

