Time-to resolution of AE (any grade) for a specific category is defined as the longest time from onset to complete resolution or improvement to the grade at baseline among all clustered AEs experienced by the subject in this category per adverse event criteria category. Events which worsened into grade 5 events (death) or have a resolution date equal to the date of death are considered unresolved. If a clustered AE is considered as unresolved, the resolution date will be censored to the last known alive date. Improvement to the grade at baseline implies that all different events in the clustered adverse event should at least have improved to the corresponding (i.e. with same preferred term) baseline grade. This measure is defined only for subjects who experienced at least one AE in the specific category.

The time-to resolution of AE (grade 3-5) for a specific category is defined similarly with an onset date corresponding to a grade 3-5 AE.

Time-to resolution of drug-related AE (any grade or grade 3-5) for a specific category is defined similarly but restricted to drug-related AE.

The time-to resolution of AE (any grade or grade 3-5, drug-related or all) where immune modulating medication was initiated is defined similarly. For data presentation not restricted to IMAE, the additional condition that the subject started an immune modulating medication during the longest AE resolution period will be applied.

Time-to resolution for a specific subcategory is defined similarly but restricted to event of this subcategory.

The algorithm for collapsing adverse event records is using the following conventions:

For each subject and specified category, the corresponding adverse event records will be collapsed when:

- 1) Multiple adverse event records have the same onset date.
- 2) The onset date of an event record is either the same day or 1 day later than the resolution date of a preceding event record (contiguous events).
- 3) The onset date of an event record is after the onset date and prior to or on the resolution date of a preceding event record (overlapping events).

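### Time to resolution of adverse events censors deaths with the event unresolved, so the Kaplan-Meier median tends to fall before the time by which half have actually resolved

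*SAP*

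**What the plan says.** The provisions that matter are all in the SAP.

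- Appendix 1 takes one value per participant and category: "the longest time from onset to complete resolution or improvement to the grade at baseline among all clustered AEs experienced by the subject".
- It settles that death is not resolution: "Events which worsened into grade 5 events (death) or have a resolution date equal to the date of death are considered unresolved".
- The handling follows, with no separate rule for participants who died: "If a clustered AE is considered as unresolved, the resolution date will be censored to the last known alive date".
- Section 7.1 sets the method: "Time-to-event variables (e.g. time-to resolution) will be analyzed using the Kaplan-Meier technique".
- Section 7.6.6.3 fixes the set analysed, "Time-to resolution analyses are restricted to treated subjects who experienced the specific events", and the statistics for select adverse events: "percentage of subjects with resolution of the longest select AE, median time-to resolution along with 95% CI (derived from Kaplan-Meier estimation) and ranges". Participants who die therefore stay in the set, and the any-grade and Grade 3-5 summaries can both contain fatal events.
- Section 7.6.7 asks for "Summaries of time-to onset and time-to resolution of non-endocrine IMAEs where immune modulating medication was initiated presented by Category", and for the endocrine counterpart. It lists no statistics, so Kaplan-Meier applies to the IMAE tables through the general rule in 7.1.

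No readable part of the SAP names a competing-risk estimator.

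**The concern.** The SAP rightly declines to count death as resolution, but censoring takes much of that back. Kaplan-Meier assumes that a censored participant would have gone on to resolve at the rate seen in those still under observation. That is a fair assumption for someone alive with the event ongoing at the data cutoff. It cannot be true of someone who has died, least of all someone killed by the event.

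These tables tell a reader how long the toxicity lasts and how reversible it is. A median that sits too early understates duration, and does so most where events last long or are often open at death.

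**Working it through.** **No plan figure to reproduce.** The documents give no resolution times and no share of participants dying with an event unresolved. Both are assumed below and shown over a range. The only document figures used are the planned median OS values, 33 months (Arm C) and 47.1 months (Arm A), from SAP section 5.

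**Check of the mortality input.** I took the stated accrual (3 per month for 4 months, then 42 per month, so 638 are reached at 4 + 626/42 = 18.9 months), exponential survival at those medians and no dropout. Expected deaths are 170.9, 210.4 and 253.3 at months 29, 34 and 40. The SAP states 165, 211 and 254, so the hazards are a fair reading of the plan.

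**Model.** Let a be the hazard of resolution and m the hazard of dying with the event unresolved, both constant.

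- Kaplan-Meier with deaths censored: proportion resolved by t is 1 − exp(−at), with median M = ln 2 / a whatever m is.
- Cumulative incidence (what Aalen-Johansen estimates): a/(a+m) × [1 − exp(−(a+m)t)].
- Time at which the cumulative incidence reaches 50%: −ln[1 − 0.5(a+m)/a] / (a+m), which exists only if a/(a+m) > 0.5.

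Since M does not depend on m, Kaplan-Meier gives a finite median even when a/(a+m), the share who ever resolve, is below one half.

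**Size by share q dying unresolved.** Put m = a·q/(1−q). The true 50% time divided by M is (1−q) × {−ln[1 − 0.5/(1−q)]} / ln 2. For q = 10% this is 0.9 × 0.811 / 0.693 = 1.05.

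| q (assumed) | Truly resolved at the KM median (nominally 50%) | True 50% time ÷ KM median |
|---|---|---|
| 2% | 49.7% | 1.01 |
| 5% | 49.2% | 1.02 |
| 10% | 48.3% | 1.05 |
| 20% | 46.4% | 1.13 |
| 30% | 44.0% | 1.27 |
| 40% | 41.1% | 1.55 |
| 50% | 37.5% | never reached |

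**Size at the planned OS hazards.** Assume a KM median of 12 months, so a = ln 2/12 = 0.0578 per month.

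- Arm C: m = ln 2/33 = 0.0210 and a/(a+m) = 0.733. Cumulative incidence at 12 months is 0.733 × (1 − e^(−0.945)) = 44.8%, and the 50% time is 14.5 months.
- Arm A: m = ln 2/47.1 = 0.0147 and a/(a+m) = 0.797. Cumulative incidence at 12 months is 46.3%, and the 50% time is 13.6 months.
- With the Arm C hazard and shorter KM medians of 1, 3 and 6 months, the 50% times are 1.01, 3.13 and 6.55 months.

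**Worked example, 20 affected participants.** Resolutions are evenly spaced over days 7 to 84 and deaths over days 4 to 25. In the last row the 4 ongoing participants are censored from day 120.

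| Deaths / ongoing / resolved | KM median (days) | Aalen-Johansen 50% time (days) | End of KM curve | End of Aalen-Johansen curve | Crude percentage |
|---|---|---|---|---|---|
| 2 / 0 / 18 | 47.8 | 47.8 | 100% | 90% | 90% |
| 4 / 0 / 16 | 48.1 | 53.2 | 100% | 80% | 80% |
| 8 / 0 / 12 | 49.0 | 70.0 | 100% | 60% | 60% |
| 4 / 4 / 12 | 63.0 | 70.0 | 74% | 60% | 60% |

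With few deaths the two medians coincide, and with more they separate in one direction only. The crude percentage agrees with Aalen-Johansen in every row.

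**The case against.** The strongest reply has four parts.

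1. Section 7.6.6.3 reports the percentage resolved next to the median. Deaths are in its denominator as unresolved, so a finite median in a category where fewer than half resolved would be visible in the same summary. This stands. A reader might infer that the select-event tables also make resolution look more likely than it is. The percentage shows that they do not. That description fits only a probability read from, or implied by, the Kaplan-Meier curve.

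2. Fatal toxicity is reported elsewhere: Grade 5 columns in 7.6.6.1 and 7.6.7, and deaths with reasons in 7.6.1. Table mock-ups are in a Data Presentation Plan that is not part of these documents. This also stands, but none of it corrects the median itself.

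3. Censoring at death gives a legitimate description of the rate of resolution while alive. That is true of the rate. It does not make the median the time by which half of affected participants resolved, which is how a median time to resolution is normally read.

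4. The size rests on assumed inputs. This stands and limits the conclusion. A reader might infer a large distortion in supposedly slow categories such as endocrine events, or work from a 24-month median, where the planned OS hazards would give 40.4% or 43.0% truly resolved instead of 50%. The documents give no resolution time for any category. Protocol section 10.3.2 also places the safety analysis at the primary endpoint analysis, about 29 months from first patient first visit. By then only those randomised in the first 5 months, 4 × 3 + 42 = 54 of 638 (8.5%), could have 24 months of follow-up.

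**Conclusion.** The point holds for the Kaplan-Meier median, and for any probability read from its curve. That median is never later, and usually earlier, than the time by which half of affected participants have resolved. It is not evidence of an inflated percentage resolved.

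Under constant hazards the true 50% time is about 1% to 5% later when 2% to 10% die unresolved, 13% later at 20% and 55% later at 40%. At 50% it does not exist, although Kaplan-Meier still gives a median. For fast-resolving events with few deaths the effect is negligible. The shares are assumptions, and the trial's own data will decide which row of the table applies.

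A reader might also infer a distorted comparison between arms. In the 12-month illustration the arms differ by 46.3 − 44.8 = 1.5 percentage points, and section 7.6.6.3 specifies no between-arm test. The tables are descriptive safety output outside the PFS, OS and ORR hierarchy, so this is a worthwhile small improvement and no threat to the trial's conclusions.

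**What to change.** In SAP 7.6.6.3, 7.6.7 and Appendix 1:

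- treat death with the event unresolved, including Grade 5, as a competing event;
- report the Aalen-Johansen cumulative incidence of resolution, with the time at which it reaches 50% or a statement that it was not reached;
- report the number who died with the event unresolved, and keep the existing percentage resolved;
- censor at the last known alive date only participants alive with the event ongoing.

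The Kaplan-Meier median can stay alongside for comparability with earlier tables. While Appendix 1 is open, one further sentence would help: the longest-cluster rule does not say how a short fatal cluster ranks against a longer resolved one in the same participant. That gap is separate from the censoring.

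The cost is SAP wording, a standard analysis and some extra output, with no new data. The small downside is less direct comparability if the Kaplan-Meier median is dropped.
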